Abbreviated Title: Combination Immunotherapy

Version Date: 05/10/2023

Abbreviated Title: Combination Immunotherapy

NIH Protocol #: 18C0005

Version Date: 05/10/2023

NCT #: NCT03315871

IBC #: RD-17-V111-09

Title: Phase II Trial of Combination Immunotherapy in Biochemically Recurrent Prostate Cancer

NCI Principal Investigator:

[name].

Genitourinary Malignancies Branch, CCR, NCI

Drug Name	PROSTVAC -V	PROSTVAC-F	CV301	MSB0011359 C (M7824)
IND Number	[REDACTED]	[REDACTED]	[REDACTED]	[REDACTED]
Sponsor	Center for Cancer Research, NCI			
Manufacturer/Supplier	[REDACTED]	[REDACTED]	[REDACTED]	[REDACTED]

PRÉCIS

Background:

- Androgen deprivation therapy (ADT) and surveillance are treatment options for prostate cancer patients with biochemical progression after localized therapy (i.e., biochemically recurrent [BCR] prostate cancer). The primary goal in these patients is to prevent morbidity from their cancer that results from disease progression and metastatic disease on conventional imaging.
- ADT can lower the PSA in these patients, but because of its substantial side effect profile and ambiguous long-term impact, it is generally deferred by most patients until there is a rapid escalation in their PSA.
- Immunotherapy presents an alternative option for these patients that is especially attractive because it is not associated with substantial toxicity. Also, since immunotherapy can have lasting effects after treatment due to a sustained activated immune response, patients will not be required to take these treatments indefinitely to potentially benefit clinically.
- Current and previous clinical trials have demonstrated that single agent immunotherapy can impact PSA in patients in this population.
- The focus of this study is to determine if combination immunotherapy with immune-cell mobilizing vaccines can initiate an immune response in the first 4 months that is then augmented by an immune checkpoint inhibitor in the following 3 months.
- In addition to PSA responses (the primary metric in this population), safety, changes in immune responses, and PSA kinetics will also be evaluated.

Objectives:

Primary Objectives:

- Safety Lead-In: To evaluate the safety and tolerability of combination immunotherapy in participants with castration-resistant prostate cancer
- Biochemical Recurrence: To determine if the combination immunotherapy can induce a 30% decline in PSA in 28% of participants with biochemically recurrent prostate cancer.

[figure not shown]

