begin C1D1 with vaccine therapy. In this case, the 3 PSA values obtained prior to enrollment will be evaluated as if they were collected during the surveillance period while enrolled and will factor into the determination of the intra-study apex value (See Section 6.3.2) highest PSA that is within 10% of another peak PSA for the participant on-study. Any other peak PSA values that are beyond 10% of other PSA values on the study will be determined as potential lab variability and excluded from response assessment.

- With Amendment v05/10/2023, participants that have at least 3 PSA measurements in the surveillance period, with at least one of them sufficient to provide the doubling time from baseline, will not undergo any further PSA measurements in the surveillance period.

Prostvac will be administered nearly identical to the Phase III dosing with Prostvac-V given day 1 (week 1) followed by Prostvac-F on weeks 3 and 5 then monthly for an additional 5 months. Therefore, Prostvac-V is given one time (priming vaccine) followed by 7 doses of Prostvac-F (booster vaccine). The administration schema for CV301 is representative of the Phase I dose escalation trial. MVA-BN-CV301 (priming vaccine) is administered on day 1 (week 1) and week 3 followed by FPV-CV301 (booster vaccine) administered on week 5 then monthly for an additional 5 months.

MSB0011359C (anti-PDL1 TGF β Trap) will be administered at the recommended phase II dose of 1200mg by IV infusion every 2 weeks for 3 months (6 doses) starting after 4 months of concurrent Prostvac and CV301.

Effective with amendment v7/29/2021, MSB0011359C will no longer be given as part of the treatment combination for the Biochemical Recurrence cohort (Arms 2 and 3). This cohort will now receive Prostvac and CV301 during months 1-7 following surveillance.

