6.3.1 Disease Progression

- PSA will not be used to measure progression of disease. Participants will be offered androgen deprivation therapy (ADT) as clinically indicated. Starting ADT will be done at the discretion of the investigator, although this will result in treatment termination and removal from the clinical trial. Participants may go on ADT at any time, although this may result in removal from the trial. PSA will be used to calculate PSA kinetics/tumor growth kinetics.
- Development of a new bone lesion on bone scan.
- Development of a soft tissue mass, identified on CT scan or physical exam, consistent with metastatic prostate cancer. If identified on physical exam, the lesion may be biopsied to confirm the presence of prostate cancer.
- Development of urethral, ureteral, or spinal cord obstruction secondary to tumor.
- Development of cytologically positive pleural effusion or lymphangitic spread in the lungs.
- Symptoms which in the opinion of the investigator are consistent with clinical progression.

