6.3.2 Intra-study PSA response

Participants will be monitored for PSA kinetics once enrolled. Participants who have an intra study decline in PSA will be evaluated for PSA response. Such responses would be defined by an intra-study apex PSA, which will be established by determining the maximum PSA value that can be validated by another intra-study PSA value within 10%. (The goal here is to not capture lab variations which may be seen as isolated PSA spikes (i.e. greater than 10%) in the context of participant follow-up. Responders will then be evaluated using confirmed PSA declines (at least 2 consecutive values after the intra-study apex) of at least 30%. Participants with intra-study PSA declines greater than 50% will also be identified.

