10.2 SAMPLE SIZE DETERMINATION

The trial will begin with a 6-participant safety lead-in. Following determination of safety, the primary objective of this study is to determine if the use of two vaccines combined with an immune checkpoint inhibitor can be associated with a modestly high fraction of participants who can experience at least a 30% decline from their maximum PSA anytime during treatment to the minimum value during treatment.

Safety data for the 6-participant lead-in will be shared with IRB before accrual commences in the biochemical recurrence cohort. Beyond safety, this cohort will just be evaluated in a descriptive manner.

Because participants may be receiving the proposed treatment and be followed for PSA changes over an extended period, and the evaluation of the endpoint may take place at any point during this potentially long period, the trial will use a single stage design for evaluating efficacy. With 25 evaluable participants who do not receive M7824, there would be 82% power to rule out 15% and be consistent with 35% who may be able to experience a 30% decline in PSA, using an exact binomial test with a 0.10 one-sided significance level. As an illustration, if 25 evaluable participants are enrolled, 7 of 25 (28.0%) who experience at least a 30% PSA change from the maximum level would have an associated one-sided lower 90% confidence interval bound of 16.3%, and simultaneously an associated one-sided upper 90% confidence interval bound of 42.6%. These demonstrate that 7/25 would be a desirable result based on the parameters selected.

With the amendment v7/29/2021, the initial 6 participants who received M7824 will be evaluated separately in exploratory fashion and will not be included among the 25 main participants.

In addition, because a trial of participants with similar eligibility (16-C-0035) may result in approximately 36 participants who are undergoing surveillance for 6 months, this other trial may serve as a control for a secondary evaluation. The changes in PSA on this trial during the initial 6 months can be compared to the changes in PSA during the initial 6 months on the surveillance arm of the control trial as a secondary evaluation. With 25 evaluable participants on this trial and 36 evaluable participants on the other trial, there would be 81% power to identify a difference between 35% of participants on this trial with a 30% PSA maximum change and 10% of participants on the

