10.4 STATISTICAL ANALYSES

10.4.1 General approach

Following a safety determination in 6 participants meeting separate eligibility requirements, the PSA decline measured from the maximal value obtained while on study to the minimum value obtained while on study will be obtained for each patient, and will be considered a success if the maximal PSA decline is 30% or more. The fraction of evaluable participants who experience at least a 30% decline will be determined. Quantitative parameters will be tested for changes over time using paired tests.

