10.4.9 Exploratory analyses

The study will aim to evaluate immune changes after treatment with 2 vaccines for 4 months.

Many immune parameters (See Section **5.1**) will be obtained at baseline and at several time points beginning at the time the two vaccines are first administered. The changes in the immune parameters after treatment with 2 vaccines for 4 months will be determined and tested for statistical significance using a two-tailed 0.05 significance level paired t-test or Wilcoxon signed rank test (if the paired differences are not normally distributed). Since there are potentially a moderately large number of these tests, they will be reported as being of secondary intent and presented without adjustment for multiple comparisons but in the context of the number of such tests performed.

Willing participants will continue to be followed after cycle 7 until progression or ADT is clinically indicated.

Patients in cohort 2 who received M7824 as part of their therapy will have their PSA response evaluated in a descriptive fashion, and may be compared informally to those from the remaining patients who do not receive M7824.

10.4.10

Halting Rules

If either of the below occurs, the Principal Investigator will halt accrual to the trial and will discuss with the NIH Intramural Institutional Review Board (IRB) whether any changes need to be made to the protocol.

- One occurrence of grade 5 toxicity by the NCI-CTCAE version 4.0 attributable to the treatment regimen.
- Two occurrences of grade 4 toxicity by the NCI-CTCAE version 4.0 attributable to the treatment regimen.
- More than two episodes of grade 3 colitis

This will apply to both cohorts—the phase I lead-in cohort and the main cohort of biochemical recurrence.

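### Read literally, section 6.3.2 lets a later PSA relapse above the old peak cancel a confirmed 30% decline, and section 10 gives other rules without saying which governs

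*Combined protocol and SAP*

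**What the plan says.** Section 6.3.2 defines an apex for each man, "which will be established by determining the maximum PSA value that can be validated by another intra-study PSA value within 10" percent, and then requires "confirmed PSA declines (at least 2 consecutive values after the intra-study apex) of at least 30" percent. Section 3.1 restates the apex as the "highest PSA that is within 10% of another peak PSA for the participant on-study". Neither section ties the apex to the period before the decline, closes the window, or says whether a confirmed response is kept.

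A PSA rise does not end participation: "PSA will not be used to measure progression of disease" (section 6.3.1). Follow-up is open-ended: "Willing participants will continue to be followed after cycle 7 until progression or ADT is clinically indicated" (section 10.4.9). Visits are monthly for the first five months after treatment and may then be 4 to 8 weeks apart (section 3.7). On ADT, the précis says that "it is generally deferred by most patients until there is a rapid escalation in their PSA".

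Section 10 words the endpoint differently:
- 10.1.1 asks for a confirmed 30% decline but does not define confirmation.
- 10.2 takes both the maximum and the minimum during treatment, yet also says that "the evaluation of the endpoint may take place at any point during this potentially long period".
- 10.4.1 uses "the PSA decline measured from the maximal value obtained while on study to the minimum value obtained while on study" and counts success if the maximal decline is 30% or more.
- 10.4.2, the primary analysis, uses maximum to minimum while on study. It mentions no apex, confirmation or time order.

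**The concern.** Section 6.3.2 is the only place that defines the confirmed decline named in 10.1.1. Its apex is a maximum over the whole study, so it can move. If PSA regrows past the old peak and the new value is validated, the apex becomes that late value. The two confirming values now come before it, and no qualifying decline remains.

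A man could thus be a responder at one data cut and a non-responder at a later one, with nothing about the earlier response having changed. Men enrolled early, who are followed longer, would be more exposed than men enrolled late. The primary analysis rests on 25 men and a boundary of 7 responders, so a few reversals could change the conclusion.

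**Working it through.** **1. The plan's own figures.** Inputs from section 10.2: n = 25, null rate 15%, target rate 35%, exact binomial test, one-sided 0.10.
- P(X ≥ 6 | 25, 0.15) = 0.1615, too large. P(X ≥ 7 | 25, 0.15) = 0.0695, so the boundary is 7.
- P(X ≥ 7 | 25, 0.35) = 0.8266. The stated 82% is reproduced.
- One-sided 90% bounds for 7/25 are 16.3% and 42.6%, as stated.

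**2. The 6.3.2 rule on one PSA series.** Assumed series: a rise to a peak of 10, then 9.8 (which validates it), 8.5, 7.4, 6.6, 6.2, 6.0, 6.0, then monthly regrowth from 6.0 with a 10-month doubling time, PSA = 6.0 × 2^(k/10) at month k of regrowth. The response threshold is 0.7 × 10 = 7.0, met by consecutive values from 6.6 onward.

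| Month of regrowth | Last PSA | Apex under 6.3.2 | Status |
|---|---|---|---|
| 0 | 6.00 | 10 | responder |
| 7 | 9.75 | 10 | responder |
| 8 | 10.45 | 10.45 (validated by 10) | non-responder |
| 14 | 15.83 | 15.83 (validated by 14.77) | non-responder |

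At other doubling times between 5 and 15 months the old peak is passed 4 to 12 months after regrowth starts, and this man ends as a non-responder in every case tried.

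**3. When regrowth can cancel a response.** A 30% decline is regrown in DT × log2(1/0.7) = 0.515 × DT months, where DT is the doubling time. For the entry range of 5 to 15 months (section 2.1.3.3) that is 2.6 months (DT 5), 5.1 (DT 10) and 7.7 (DT 15), if regrowth runs at the entry rate.

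**4. Limit: the new peak must be validated.** Taking 10% of the lower value, two consecutive monthly values validate each other only if 2^(1/DT) ≤ 1.10, that is DT ≥ 7.3 months (6.6 if 10% of the higher value is used). At 8-week spacing, taken as two months, the first threshold doubles to 14.5 months. With faster regrowth, a new apex needs a value close to the old peak. In noise-free simulated series (peak 10, nadir uniform from 4 to 7, monthly visits, followed three visits past the old peak), the share of relapsers losing status was 100% at doubling times of 7 to 15 months, 93% at 6 and 76% at 5.

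**5. The same man under section 10.**
- Maximum to minimum, order ignored: success.
- Largest fall at any time: success.
- Minimum required after the overall maximum: failure.
- Treatment-only window (10.2): relapse after treatment is not counted.

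**6. The unordered reading on a PSA that only rises.** The first value is the minimum and the last is the maximum. The minimum is at most 70% of the maximum once DT × log2(1/0.7) months have passed, which again gives 2.6 to 7.7 months. A man with no decline at all would be a success.

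**7. Effect on power if 6.3.2 governs.** Let f be the assumed share of true responders who lose status. The observed rate is 0.35 × (1 − f).

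| f | Rate | P(X ≥ 7 of 25) |
|---|---|---|
| 0 | 35.0% | 82.7% |
| 10% | 31.5% | 71.7% |
| 20% | 28.0% | 57.5% |
| 30% | 24.5% | 41.6% |

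**The case against.** The strongest reply is that 6.3.2 is not the primary-analysis text. Section 10.4.2 is, and read without time order it keeps a relapsing responder as a success, because a higher late maximum only widens the gap. The maximal decline in 10.4.1 is naturally the largest fall, which regrowth cannot undo. The 82% in 10.2 belongs to an endpoint confined to treatment. This stands. A reader might infer that the response rate is biased down and the stated power is not delivered, but the documents support that only if 6.3.2, or a time-ordered whole-study reading of section 10, governs. No section says so, and the unordered reading errs upward.

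A reader might also infer that every relapser is lost. That does not follow. The new peak needs validation, starting ADT takes a man off study (sections 3.6.2 and 6.3.1), only willing men are followed after cycle 7, and the précis expects lasting effects after treatment. Nor does the plan instruct anyone to withdraw a response. The reversal comes from applying 6.3.2 to the full series, and the authors may well intend any confirmed decline to count.

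The reply does not remove the problem. Section 6.3.2 alone defines the confirmation that 10.1.1 asks for, nothing says which rule governs, and the reading that rescues the relapser also credits a PSA that never fell. If the intended rule differs from the literal one, it needs to be written down before analysis.

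**Conclusion.** The point holds in conditional form. Applied literally to the full on-study series, 6.3.2 can turn a confirmed responder into a non-responder through later regrowth, so response status depends on length of follow-up. Whether this reaches the primary result depends on which of the conflicting rules in 6.3.2, 10.2 and 10.4.1-10.4.2 is used, and the plan does not say.

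The sample-size arithmetic is correct. The power figures of 71.7%, 57.5% and 41.6% rest on two assumptions: that 6.3.2 governs, and that 10%, 20% or 30% of responders are lost. The documents give no durability of response from which to estimate that share, so the figures show sensitivity and are not a forecast. The need for one stated rule does not depend on them.

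**What to change.** Use one rule in 6.3.2, 10.2, 10.4.1 and 10.4.2, and align section 3.1 with it. Suggested wording: *A participant is a responder if two consecutive PSA values within the stated evaluation window are each at least 30% below the highest earlier PSA value that is validated by another value within 10%, where the apex and its validating value both precede the two confirming values. Once met, response status is not changed by later PSA values.*

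State the window once. Section 10.2 says during treatment and 10.4 says while on study, and these must be reconciled. The same sentence should settle whether surveillance values may supply the apex, as section 3.1 allows.

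In the worked series this rule keeps the man as a responder at every month of regrowth, and it does not credit a smoothly rising PSA. The cost is a few sentences of text and a small change to the derivation program, with no new visits or data. The downside is a slightly higher false-response rate when PSA is noisy. In simulated records of pure growth over 24 months, the rule scored 0% at a noise CV of 5% or 10% and about 0.5% at 15%, against roughly 0.1% to 0.2% for the literal 6.3.2 rule at 15%.

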6.4 TOXICITY CRITERIA

The following adverse event management guidelines are intended to ensure the safety of each participant while on the study. The descriptions and grading scales found in the revised NCI Common Terminology Criteria for Adverse Events (CTCAE) version 4.0 will be utilized for AE reporting. All appropriate treatment areas should have access to a copy of the CTCAE version 4.0. A copy of the CTCAE version 4.0 can be downloaded from the CTEP web site (http://ctep.cancer.gov/protocolDevelopment/electronic_applications/ctc.htm#ctc_40).

7 NIH REPORTING/DATA AND SAFETY MONITORING PLAN

7.1 DEFINITIONS

Please refer to definitions provided in Policy 801: Reporting Research Events found at:
<https://irbo.nih.gov/confluence/pages/viewpage.action?pageId=36241835#Policies&Guidance-800Series-ComplianceandResearchEventReportingRequirements>.

7.2 OHSRP OFFICE OF COMPLIANCE AND TRAINING/IRB REPORTING

7.2.1 Expedited Reporting

Please refer to the reporting requirements in Policy 801: Reporting Research Events and Policy 802 Non-Compliance Human Subjects Research found at:

<https://irbo.nih.gov/confluence/pages/viewpage.action?pageId=36241835#Policies&Guidance-800Series-ComplianceandResearchEventReportingRequirements>. Note: Only IND Safety Reports that meet the definition of an unanticipated problem will need to be reported per these policies.

7.2.2 IRB Requirements for PI Reporting at Continuing Review

Please refer to the reporting requirements in Policy 801: Reporting Research Events found at:
<https://irbo.nih.gov/confluence/pages/viewpage.action?pageId=36241835#Policies&Guidance-800Series-ComplianceandResearchEventReportingRequirements>.

7.3 NCI CLINICAL DIRECTOR REPORTING

Problems expeditiously reviewed by the OHSRP in the NIH eIRB system will also be reported to the NCI Clinical Director/designee; therefore, a separate submission for these reports is not necessary.

In addition to those reports, all deaths that occur within 30 days after receiving a research intervention should be reported via email unless they are due to progressive disease.

To report these deaths, please send an email describing the circumstances of the death to [contact] within one business day of learning of the death.

7.4 INSTITUTIONAL BIOSAFETY COMMITTEE (IBC) REPORTING CRITERIA

7.4.1 Serious Adverse Event Reports to IBC

The Principal Investigator (or delegate) will notify IBC of any unexpected fatal or life-threatening experience associated with the use of PROSTVAC Vaccine as soon as possible but in no event later than 7 calendar days of initial receipt of the information. Serious adverse events that are unexpected and associated with the use of the PROSTVAC Vaccine, but are not fatal or life-threatening, much be reported to the NIH IBC as soon as possible, but not later than 15 calendar days after the investigator's initial receipt of the information. Adverse events may be reported by using the FDA Form 3500a.

7.4.2 Annual Reports to IBC

Within 60 days after the one-year anniversary of the date on which the IBC approved the initial protocol, and after each subsequent anniversary until the trial is completed, the information described below shall be submitted. Alternatively, the IRB continuing review report can be sent to the IBC in lieu of a separate report. Please include the IBC protocol number on the report.

7.4.2.1 Clinical Trial Information

A brief summary of the status of the trial in progress or completed during the previous year. The summary is required to include the following information:

- the title and purpose of the trial
- clinical site
- the Principal Investigator
- clinical protocol identifiers
- participant population (such as disease indication and general age group, e.g., adult or pediatric);
- the total number of participants planned for inclusion in the trial; the number entered into the trial to date whose participation in the trial was completed; and the number who dropped out of the trial with a brief description of the reasons
- the status of the trial, e.g., open to accrual of subjects, closed but data collection ongoing, or fully completed,
- if the trial has been completed, a brief description of any study results.

